Feelings about Exercise: Protocol

NCT03598647

1/23/19

Background and objectives

Despite the numerous health benefits of regular physical activity (PA), >50% of adults are insufficiently active. Understanding why some individuals choose to engage in PA while others do not is important for informing the development of future PA interventions. Previous research has demonstrated that those who have more positive affective responses to exercise (i.e., the pleasure or displeasure experienced with PA) are more likely to exercise in the future. However, an interesting paradox is that most people generally 'feel good' post-exercise. This begs the questions, if exercise makes people feel good, why don't more people exercise? The answer may lie in one's memory of how exercise makes them feel.

This study seeks to compare exercisers and non-exercisers on their affective responses to exercise, which includes pre-, during, and post-exercise affect, memory of during and post-exercise affect, and anticipated affect towards a future exercise session. It is hypothesized that compared to regular exercisers, non-exercisers will have a more negative memory of how exercise made them feel, and as a result, also have more negative anticipated affect towards a future exercise session. Further, this study seeks to pilot an intervention to improve affective response to exercise among the group of non-exercisers. It is hypothesized that non-exercisers randomized to an affect-based intervention will have a more favorable affective response to exercise following the intervention compared to those randomized to the control intervention (e.g., basic PA recommendations).

Participants

A total of 59 individuals with overweight/obesity (BMI 25-40 kg/m²), who were weight loss seeking, and between the ages of 18-60 were recruited via self-referral from Internet advertisements. Interested individuals completed a phone screen questionnaire to determine initial eligibility. During this screening, trained research assistants queried potential participants on their moderate-to-vigorous intensity PA (MVPA) over the previous 6 months and a recent 'typical' week. If average MVPA was <30 min/week, the individual was classified as a 'non-exerciser', if average MVPA was ≥150 min/week, the individual was classified as an 'exerciser'. Individuals reporting an intermediate amount of MVPA (30 to <150 min/week) were ineligible for this study as the goal was to target distinctive groups of exercisers vs. non-exercisers. Exclusion criteria included conditions limiting ability to exercise, history of coronary artery disease (i.e., myocardial infarction), stroke, diabetes, pulmonary disease (e.g., COPD), uncontrolled hypertension (i.e., resting BP ≥140/90 mmHg), use of any medication that would affect heart rate (HR; e.g., beta blocker), current enrollment in a weight loss treatment program, history of bariatric surgery, or women who were nursing/pregnant,

Study overview

Individuals deemed eligible based upon the phone screen attended an in-person orientation session in order to learn about the study in greater detail and to provide informed consent in accordance with guidelines set forth by the Internal Review Board of the Miriam Hospital. Upon consenting, participants completed a baseline assessment, which included measures of BMI, fitness, and 1 week of objective physical

activity (PA) monitoring. Participants then returned to the laboratory for Exercise Session 1, in which they walked on a treadmill for 30 minutes at a moderate intensity. Prior to exercise they reported on anticipated affect (i.e., how they expect the upcoming exercise bout to make them feel), and momentary affect was assessed before, during, and after exercise. In days 1, 3, and 7 following the exercise session, participants were asked to report on their recalled affect via text messaging. They then returned to the laboratory to complete an identical exercise session (Exercise Session 2). Following the completion of the final post-exercise affect measurement, 'non-exercisers' randomly received 1 of 2 PA interventions and then completed additional study measures (described in detail below), while 'exercisers' did not complete any additional study procedures beyond this point.

Baseline Visit: BMI, Fitness Test, Objective PA Measurement: Prior to participating in Exercise Sessions 1 and 2, participants completed the following baseline assessment measures.

BMI. Weight was measured to the nearest 0.1 kg using a calibrated digital scale and height was measured to the nearest 0.1 cm using a wall-mounted stadiometer. Body mass index (BMI) was calculated as kg/m^2 .

Fitness Test. Fitness was measured via a sub-maximal graded exercise test (GXT). Participants walked on the treadmill at 3.0 mph and the speed and incline were increased every three minutes until 75% of age-predicted maximal HR was achieved. Total time spent on the treadmill (in seconds) was used as an indicator of fitness. The purpose of this GXT was to allow participants to gain familiarity with walking on a treadmill and assist in determining the starting treadmill grade for the following exercise visit.

Objective PA Measurement. While participants were deemed eligible for this study based upon self-report measures of PA, direct PA monitoring was also performed to confirm that 'exercisers' and 'non-exercisers' significantly differed on MVPA. All participants wore a previously validated activity monitor (Sensewear Armband, Body Media Inc., Pittsburgh PA) for 1 week and were asked not to alter their activity levels during this period. The monitor is worn on the upper arm and assesses movement and energy expenditure, however the device does not provide any information or feedback to participants. Minute-by-minute data were collected, and using proprietary algorithms, MET values were computed for each minute the device was worn. Exercise groups were compared on time spent engaging in bout-related MVPA (≥ 3 METs, ≥ 10 min).

Exercise Session 1

Exercise Protocol. Following completion of all assessment measures, participants returned to the laboratory for Exercise Session 1. Upon arrival, participants were given a detailed description of the upcoming exercise protocol and were equipped with a HR monitor. Immediately prior to the start of the exercise bout, participants were asked to report their pre-exercise *momentary* affect using the Feeling Scale and their *anticipated*

affect towards the upcoming exercise bout using a visual analogue scale (see below for additional detail on affect measures). They then completed the exercise protocol which consisted of a 2-minute warm-up, followed by 30 minutes of moderate-intensity walking (70-75% of age-predicted maximal HR), and a 2-minute cool-down. This exercise duration and intensity was chosen because it is consistent with the American College of Sports Medicine's exercise guidelines, and is feasible for individuals with overweight/obesity. Starting exercise intensity was estimated using HR data from the baseline fitness test. Heart rate was monitored every minute and the treadmill grade or speed was adjusted by trained research staff if the subject's HR fell outside the target range for two consecutive minutes. Affect was assessed every 5 minutes during exercise, immediately post-exercise, and 15 minutes following the completion of the exercise bout.

Assessment of momentary affect. The Feeling Scale (FS; Hardy & Rejeski 1989) was used to assess momentary affect before, during and after exercise. This single-item measure asks participants to rate how they feel 'at the present moment' on an 11-point scale ranging from -5 (very bad) to +5 (very good). *Pre-exercise* affect was assessed as individuals stepped onto the treadmill but before the exercise was started. *During* exercise affect was assessed every 5 minutes during the exercise bout (excluding warm-up), and *post-exercise* affect was assessed immediately after the conclusion of the exercise protocol and exactly 15 minutes later.

Assessment of anticipated affect. Prior to the exercise sessions *anticipated affect* was assessed using a 100mm visual analog scale (VAS). This method for assessing anticipated affect requires participants to denote their response on a continuous line (anchored by 'very bad' and 'very good' similar to the Feeling Scale used for measuring current affect) but does not quantify affect with a numerical response (e.g., "2"), thereby eliminating potential for participants to provide subsequent affect ratings that are simply repetitions of their predictions. Participants were specifically asked "How do you anticipate feeling during exercise?" and "How do you anticipate feeling after exercise?".

Affective Recall and Memory Bias

In the week following Exercise Session 1, all participants were asked to maintain their typical daily routines of either exercising or not exercising and respond to an online questionnaire assessing their recall of their own affective responses to the exercise session. These questionnaires were completed 1, 3, and 7 days following the exercise session, and participants responded to the questionnaire by clicking on a link provided via text message. In order to avoid direct recall of responses provided on the Feeling Scale, a VAS was used. On days 1, 3, and 7, participants were asked to reflect upon their Exercise Session 1 by responding to following question; "How do you remember feeling overall?" and this was considered an indicator of *global* affective recall. Following this response on day 7 only, participants were asked to further delineate how they remembered feeling during exercise, and post-exercise. Memory bias was assessed by converting VAS recall values to corresponding FS values and then taking the discrepancy between recalled and actual FS values during and post-exercise (e.g., recalled during exercise affect [assessed 7 days post-exercise] minus actual during

exercise affect [average of Feeling Scale scores every 5 minutes during exercise]. A negative number indicates that participants remembered feeling less positive during exercise than they actually felt. Memory bias for post-exercise affect was computed in a similar manner.

Exercise Session 2

In order to collect data on anticipated affect after participants had experienced one laboratory exercise session, all participants were asked to return to the laboratory for a second exercise session at least 1 week following Exercise Session 1. Exercisers were compensated \$50 for participation in the study, while non-exercisers were randomized, and received a brief PA intervention (described below).

Randomized Controlled Trial for Non-Exercisers

Immediately following Exercise Session 2, all non-exercisers were randomized to a brief, affect-based PA intervention (INT; n=15) or an educational PA intervention, which served as the control condition (CON; n=15).

Components common to both the Affect Intervention and Control Condition. Participants in both arms were informed of the national PA guidelines (150 min/wk of MVPA) and were encouraged to meet these guidelines. They were also provided with general information regarding the physiological and psychological health benefits of regular exercise. They were educated on what types of activities were considered moderate-intensity and how to gauge this intensity on their own. Finally, they were asked to reflect on their reasons for wanting to become more physically active.

Affect Intervention. In addition to the educational content described above, participants assigned to this group received a brief, affect-based intervention with a PhD-level interventionist in which they were taught cognitive strategies designed to make their affective recall more positive. First, each participant was shown a graph of normative data from studies using the Feeling Scale during and post-exercise. This was used in the current study specifically to normalize the experience of reductions (“dips”) in positive affect during exercise and to highlight the general positive affect produced by moderate-intensity exercise. The interventionist then shared a graph illustrating the participant’s own affective trajectory from Exercise Session 1. The interventionist discussed this trajectory with the participant, pointing out the moments that were most positive, and using open-ended questions to probe the participants’ feelings about these moments and these data. Participants were then shown on the graph their recalled affect for the same exercise session. Time was spent pointing out discrepancies or biases in recalled affect and actual affect. Participants were asked specific questions aimed at increasing their awareness of their recall (e.g., why do you think you remembered exercise in this way? When you report on how you remember feeling in response to exercise, what do you think sticks out most in your mind and contributes to your response? Do you think you are focusing more on how you felt during or after exercise?). Third, adopting strategies from positive psychology to draw participants’ attention to positive outcomes from a bout of exercise, participants were asked to write down any positive feelings they experienced during or as a result of the previous

exercise session (e.g., improved mood, feeling energized, feeling accomplished/proud, or feeling good about doing something beneficial for the body). They then shared their responses with the interventionist and participants were encouraged to think about these positive experiences, feelings, and motivations for engaging in exercise often, and specifically during the next exercise session.

Post-intervention assessment

Non-exercisers in both arms were informed they could increase their PA following Exercise Session 2 if they desired, and they were given the Sensewear armband to wear for 1 week to objectively assess whether there was an intervention effect on bout-related MVPA. Further, during the week following Exercise Session 2, all non-exercisers were asked to complete recalled affect questionnaires for Exercise Session 2 at 1, 3, and 7 days following the session, as was done previously.

Exercise Session 3

One to two weeks following Exercise Session 2, non-exercisers from both the control and intervention groups returned to the laboratory for a third exercise session (Exercise Session 3). This session was identical to the previous exercise sessions and measures of anticipated affect, pre-, during, and post-exercise affect were obtained. All non-exercisers attending Exercise Session 3 (INT and CON) were compensated \$50 for their time.

## **Statistical analysis**

Preliminary analyses were conducted to compare the groups (exercisers vs. non-exercisers) with respect to demographic variables including age, BMI, and gender. Chi Square tests were used to assess between-group differences in categorical variables and independent two-sample t-tests were used for continuous variables. First, unadjusted between-group differences in anticipated affect, pre-exercise affect, and post-exercise affect were assessed using independent two-sample t-tests. Next, using a series of longitudinal linear mixed effects models, we examined between-group (exercisers vs. non-exercisers) differences in serial measures of during-exercise affect (5, 10, 15, 20, 25 minutes) and post-exercise affect (immediate and 15 minutes post-exercise). Models included a subject-specific intercept and adjusted for repeated measures within participant over time. A similar analytic strategy was used to examine group differences in recalled affect (1, 3, and 7 days post-exercise). The goal was to determine the degree to which global recalled affect is associated with (i.e., biased toward) affective responses during or after PA and whether this differs between exercisers and non-exercisers. Correlation analysis was used to examine whether affective recall bias was correlated with anticipated affect towards future exercise. Finally, between-subjects ANOVAs were used to compare non-exercisers receiving the brief cognitive intervention to those in the control group on anticipated affect, affective response to exercise session 3, recalled affect for exercise session 2, and minutes/week spent in MVPA (assessed via the armband). All analyses were carried out in SAS 9.3 with significance level set at .05 a priori. Mixed effects models use a likelihood based approach to estimation, thus making use of all available data without directly imputing missing value.

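### Anticipated affect is measured before and after the Session 1 experience, but no planned analysis separates a group gap that already existed from one that arose afterwards

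*SAP*

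**What the plan says.** The protocol's Background and objectives predicts that non-exercisers will have a more negative memory of exercise "and as a result, also have more negative anticipated affect towards a future exercise session". The sentence contains a difference in level (non-exercisers expect less) and a direction of cause (because of what they remember).

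The design supplies two measurements of anticipation. For Session 1, the Study overview states: "Prior to exercise they reported on anticipated affect". The section on Exercise Session 2 gives that session's purpose: "In order to collect data on anticipated affect after participants had experienced one laboratory exercise session". Both use the two visual analogue items described under Assessment of anticipated affect, one for feelings during exercise and one for feelings after it.

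The SAP (Statistical analysis) handles the group difference in anticipation in one clause: "unadjusted between-group differences in anticipated affect, pre-exercise affect, and post-exercise affect were assessed using independent two-sample t-tests". It does not say whether this refers to Session 1, Session 2 or both. The mixed models that follow cover during-exercise, post-exercise and recalled affect; anticipated affect is not among them. The link to memory has its own line: "Correlation analysis was used to examine whether affective recall bias was correlated with anticipated affect towards future exercise". No covariates are stated for it.

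**The concern.** The two groups are not randomised. They are opposite ends of self-reported activity (under 30 against at least 150 min/week), with the middle range excluded to make them distinct. A difference in expectation before any study session is therefore plausible, although the documents give no figure for it.

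A t-test at Session 1 comes before any memory of the study bout. A t-test at Session 2 combines whatever gap existed before Session 1 with whatever changed after it. Running both would display an earlier gap but would not test the change. The design has the paired values needed to separate the two components, and the plan does not use them.

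At stake is how much of the prediction the trial can address. As planned, it can report that non-exercisers expect less. It has little basis for saying whether that expectation moved after the session whose recall was measured.

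**Working it through.** **Inputs from the documents.** Total 59 participants; non-exercisers 15 + 15 = 30; exercisers 59 − 30 = 29 (by subtraction, not stated). Significance level .05. The documents give no power calculation, SD or effect size for anticipated affect, so there is no planned figure to reproduce.

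**Assumptions.** Two-sided testing; complete data; unit SD at both sessions; gaps of 0.3, 0.5 and 0.8 SD; within-group correlation r between sessions of 0.5 to 0.9. None of these is in the documents.

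**Step 1: Session 2 t-test when the gap is identical at both sessions.**
SE = √(1/29 + 1/30) = 0.260 SD, df = 57. Noncentrality = gap / SE.

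| Gap (SD) | Noncentrality | Probability significant |
|---|---|---|
| 0.3 | 1.15 | 0.21 |
| 0.5 | 1.92 | 0.47 |
| 0.8 | 3.07 | 0.86 |

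A level gap truly exists in every row, so these are power values.

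**Step 2: test of change in the same scenarios.** With two sessions and complete data, the group-by-session test is the t-test on each participant's Session 2 minus Session 1 difference. In 20,000 simulated trials per setting, with gaps of 0 to 0.8 SD and r = 0.5, 0.7 and 0.9, it rejected in 4.6% to 5.2% of runs. That is its nominal level, because nothing changed.

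**Step 3: what the change test can detect.** Its SE is √(2(1 − r)) times that of the single-session comparison. The single-session difference detectable with 80% power is 0.742 SD.

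| r | SE ratio | Detectable change in gap (SD) | Power for a 0.3 SD change |
|---|---|---|---|
| 0.5 | 1.00 | 0.74 | 0.21 |
| 0.7 | 0.77 | 0.57 | 0.31 |

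The r = 0.7 power comes from noncentrality 0.3 / (0.775 × 0.260) = 1.49. The two tests have different targets, so the SE ratio does not make one a better version of the other.

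**Step 4: does the planned correlation fill the gap?** Suppose it pools both groups, recall bias and anticipation are unrelated within each group, and each differs between groups by 0.5 to 0.8 SD. The mean correlation is then 0.06 to 0.14 and the test rejects in 7% to 18% of runs. Group membership alone can produce an association.

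**Step 5: is adjusting for Session 1 anticipation enough for the group comparison?** Not in these non-randomised groups. With an unchanged gap, analysis of covariance leaves a residual group difference of gap × (1 − r). For 0.5 SD and r = 0.7 this is 0.5 × 0.3 = 0.15 SD. Across r = 0.5 to 0.9 it rejects in 7% to 18% of runs at 0.5 SD, and in 10% to 36% at 0.8 SD. The change contrast is therefore the cleaner addition.

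**The case against.** The strongest reply is that the SAP never gives the t-test the causal claim. It is introduced as a first, unadjusted comparison, the protocol does predict a difference in level, and a t-test answers that. Memory is examined by the models for recalled affect, and its link to anticipation by the correlation. All of this stands. A reader might infer that the t-test would by itself confirm the memory explanation, or that 47% and 86% are false-positive rates. The documents support neither: nothing says the t-test alone establishes cause, and rejecting equality when a gap exists is correct.

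A second reply is that the change in gap should not become the test of the causal claim. That also stands. The group-by-session model contains no memory variable, and novelty of the bout, regression to the mean or limits of the scale could move the gap. The protocol's motivation is also memory of exercise in general, so memories of earlier exercise could already have produced a gap at Session 1. A stable gap would not refute that.

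A third reply is that the t-test may be run at both sessions. An earlier gap would then be visible, but the change would still be untested.

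What remains is that neither the t-test nor the correlation, as written, separates an earlier gap from a later one.

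**Conclusion.** The point holds as a limited, inexpensive improvement; it is not a fault that invalidates the planned comparison. The Session 2 t-test is a sound test of whether non-exercisers expect less. It is not evidence that anything changed after Session 1, and the correlation with recall bias, with no stated adjustment for Session 1 anticipation or group, does not supply that evidence.

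How much this matters depends on the size of any gap before Session 1, which the documents do not give. The range of 21% to 86% rests on assumed gaps of 0.3 to 0.8 SD, two-sided testing and 29 exercisers. The structural point, that one session's difference cannot be split into an earlier and a later part, needs none of these assumptions.

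**What to change.** 1. State the session for each anticipated-affect comparison, and keep the Session 2 group comparison as the test of level.
2. Add one mixed model per item (during, after) with group, session (1, 2), group by session and a participant intercept. Report the change in the group gap with its 95% CI.
3. Add Session 1 anticipation and group to the analysis relating recall bias to Session 2 anticipation.
4. State how results will be read. A Session 2 gap alone supports lower expectation in non-exercisers. It is attributed to memory of the study session only if both the change in gap and the adjusted recall-bias association support that. A non-significant change is inconclusive. A stable gap does not rule out an effect of memories of earlier exercise.

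**Cost.** SAP wording, one extra model per item and two covariates; no new data. The analyses are reported in the past tense, so this would be a supplementary re-analysis, labelled as such. Power for a modest change is limited, and even a changed gap would not prove that memory is the cause. Session 1 anticipation also follows the baseline treadmill test, so the contrast covers only what happened from the 30-minute bout onward.

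### Does modelling during-exercise affect at 5 to 25 minutes leave out the last rating of a 30-minute walk?

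*SAP*

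**What the plan says.** The SAP, under Statistical analysis, plans mixed models with a subject-specific intercept to compare exercisers and non-exercisers on "serial measures of during-exercise affect (5, 10, 15, 20, 25 minutes" and on "post-exercise affect (immediate and 15 minutes post-exercise".

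The protocol, under Exercise Session 1, describes the bout as a "2-minute warm-up, followed by 30 minutes of moderate-intensity walking (70-75% of age-predicted maximal HR), and a 2-minute cool-down". It gives the rating schedule as follows: "Affect was assessed every 5 minutes during exercise, immediately post-exercise, and 15 minutes following the completion of the exercise bout".

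Under Assessment of momentary affect, the protocol says that "exercise affect was assessed every 5 minutes during the exercise bout (excluding warm-up", and that post-exercise "affect was assessed immediately after the conclusion of the exercise protocol and exactly 15 minutes later".

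Under Affective Recall and Memory Bias, actual during-exercise affect is the "average of Feeling Scale scores every 5 minutes during exercise". Only the SAP lists the rating minutes.

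**The concern.** Counting in fives through a 30-minute walk suggests ratings at 5, 10, 15, 20, 25 and 30 minutes, and the SAP list stops at 25. The protocol names only the warm-up as excluded. Its immediate post-exercise rating appears to follow the cool-down, so that rating would not obviously replace one taken at minute 30 under load.

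If a minute-30 rating was collected, two things could go wrong. First, the model would omit the reading at which any fall in affect has had longest to develop; the protocol's Affect Intervention section does expect affect to dip during exercise. Second, during-exercise affect would mean five ratings in the group comparison and six in the memory-bias score. The study asks whether recall leans towards how people felt during or after exercise, so the boundary between the two matters.

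**Working it through.** The documents give no figure to reproduce on this point. The check is a reading of the schedule, followed by the size of the effect if a sixth rating existed.

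**1. What the schedule implies.** The inputs are a 2-minute warm-up, a 30-minute walk and a 2-minute cool-down (Protocol, Exercise Session 1), with ratings every 5 minutes.

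- Endpoint excluded: 5, 10, 15, 20, 25, which is five ratings and exactly the SAP list.
- Endpoint included: 5, 10, 15, 20, 25, 30, which is six ratings, one more than the SAP list.

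Both readings fit the protocol's wording. On the first, nothing is omitted and the model and the memory-bias average use the same ratings. On the second, they could differ by one rating.

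**2. Effect on a person's mean.** Let *d* be the minute-30 rating minus the mean of the 5-25 ratings. Adding the sixth rating moves the mean by *d*/6. The documents give no value for *d*, so these are assumptions:

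| *d* (Feeling Scale points) | Shift in mean, *d*/6 |
|---|---|
| -0.5 | -0.08 |
| -1 | -0.17 |
| -2 | -0.33 |
| -3 | -0.50 |

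For a steady fall of *s* points per 5 minutes, the five-rating mean lies 3.0*s* below the starting level and the six-rating mean 3.5*s* below it. The difference is 0.5*s*, or 0.10 to 0.25 points for an assumed *s* of 0.2 to 0.5. This agrees with the rule above, since *d* = -6*s* + 3*s* = -3*s* and *d*/6 = -0.5*s*.

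**3. Effect on the planned comparison.** The SAP compares groups. With complete data, the difference between group means moves by (*d* in exercisers minus *d* in non-exercisers)/6. If both groups fall equally, this is zero. If the two values of *d* differ by 1 point (assumption), it is 1/6 = 0.17 points.

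**4. Effect on memory bias.** Bias is recalled minus actual affect, so a sixth rating would move each person's during-exercise bias by -*d*/6. If *d* were the same for everyone, the correlation between bias and anticipated affect would not change.

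**5. Effect on precision.** The variance of a mean of *k* ratings, relative to one rating, is (1 + (*k* - 1)ρ)/*k*, where ρ is the assumed within-person correlation.

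- ρ = 0.5: 0.6000 with five ratings and 0.5833 with six; SD ratio √(0.6000/0.5833) = 1.014.
- ρ = 0.9: 0.9200 with five and 0.9167 with six; SD ratio 1.002.

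The SD of a person's mean would therefore differ by 0.2% to 1.4%.

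**6. Slope over the bout.** In 5-minute units, the sum of squared deviations of time is 10.0 for five points and 17.5 for six. The within-person part of a slope's standard error would be √(10.0/17.5) = 0.756 times as large, or 24% smaller. The SAP names neither a linear time slope nor a group-by-time term, so this gain belongs to a test that the plan does not describe.

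**The case for a change.** The best case for a change is that six ratings is a natural reading. Only the warm-up is excluded by name. The protocol's description of the exercise session includes the cool-down, and the immediate post-exercise rating comes after that protocol ends, so at about walking minute 30 + 2 = 32. On the five-rating reading, nothing is recorded between minute 25 and about minute 32, a 7-minute gap that sits awkwardly with ratings every 5 minutes. An analyst could average five or six ratings for memory bias and comply with the text either way, and listing the minutes would cost one sentence.

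Part of this stands. Minute 30 is unaccounted for, and the documents do not settle whether the immediate post-exercise rating comes before or after the cool-down. The protocol is loose here: one section times the 15-minute rating from the end of the bout, the other from the end of the exercise protocol.

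The step from there to an error does not stand. A late post-exercise rating does not show that a separate minute-30 rating was taken. The memory-bias definition names no minutes, so it does not contradict the SAP. The Affect Intervention section expects dips but does not place them at the end of the walk. Both documents describe the procedures in the past tense; if no such rating was recorded, none can be added to the model.

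**Conclusion.** No change follows. This is a missing detail that an analyst fills sensibly: the SAP gives the only list of minutes, and the same five ratings serve for both the mixed model and the memory-bias average. Used in that way, the plan has a single definition of during-exercise affect and gives a sound between-group comparison.

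This rests on reading the SAP list as the ratings taken during the walk, which the protocol's wording allows but does not confirm. If a minute-30 rating under load was recorded after all, the consequence is likely to be small: one-sixth of its distance from the 5-25 mean for each person, no effect on the group contrast when the change is common to both groups, and 0.17 points if the groups differ by an assumed 1 point at that reading. Only a large divergence between groups confined to the last minutes would matter more, and nothing in the documents points to one. The minutes listed concern the exerciser versus non-exerciser comparison; the SAP's description of the randomised comparison lists none.
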